16.1. Primary Efficacy

16.1.1. Primary Efficacy Variable and Derivation

The primary efficacy endpoints will compare etrasimod to placebo for:

- The proportion of subjects achieving clinical remission at Week 52

Clinical remission is defined in Section 15. The SF, RB, and ES subscores will be based on the Mayo Clinic Score eCRF. Subjects who achieve clinical remission will be referred to as responders. Subjects who do not achieve clinical remission will be referred to as non-responders.

There will be no adjustments for multiplicity as discussed in Section 8.4.

16.1.2. Missing Data Methods for Primary Efficacy Variable

Subjects who 1) discontinue the study for lack of efficacy, or adverse event related to UC, 2) initiate a rescue medication for UC, 3) have an increase in dose over Baseline levels in their existing UC medication, or 4) have rescue medical procedure (e.g., colectomy, ileostomy, or sigmoidectomy) during the study as confirmed after blinded review by clinical and medical team members before study unblinding will be considered to have a known (i.e., non-missing) outcome of nonresponse in the analysis of all efficacy endpoints at any subsequent timepoints, including the primary endpoint. The rescue medications will be identified by the Arena clinical team during blinded data review. Refer to APPENDIX 6APPENDIX 6 for the definition of rescue therapies (medication and medical procedures). In scenarios #2 and #3 above, if a subject has efficacy measurement collected after the initiation or dose increase from Baseline of UC medication, the observed data will be censored at the time of initiation or dose increase and they will be considered having a nonresponse. Subjects in all 4 scenarios above may still be included in the respective Per Protocol Set, provided they do not violate other criteria for Per Protocol Set. For example, they will be excluded from the respective Per Protocol Set if they initiate a prohibited medication before Week 52 efficacy assessment that can affect efficacy of the study

treatment and the indication is unrelated to UC.

Analysis visits will be mapped as per Section 6.4 before any missing data imputation method is applied.

Subjects with missing efficacy outcome will be included in the primary analyses using single imputation as nonresponder. Supplementary analyses of efficacy outcomes will be performed in modified Full Analysis Set with data as observed.

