5. REMOVAL OF SUBJECTS FROM STUDY TREATMENT OR ASSESSMENT

5.1. Discontinuation from Study Treatment

A subject's double-blind treatment may be discontinued for any of the following reasons:

- Worsening of disease (Note: If a subject discontinues double-blind treatment at any time, the subject may be eligible to enter the APD334-303 OLE study [Section 5.1.1])
- Adverse event that in the judgement of the Investigator and/or Medical Monitor the subject should not continue study treatment
- Subject noncompliance with the protocol or study treatment that is considered significant by the Medical Monitor
- Investigator decision
- Withdrawal by subject or parent/guardian
- Lack of efficacy
- Lost to follow-up
- Study termination by Sponsor
- Other, non-adverse event

A subject's double-blind treatment must be discontinued for any of the following reasons:

- Decline in PFT values (forced expiratory volume at 1 second [FEV₁] and/or forced vital capacity [FVC]) below 50% of the predicted values
- Confirmed diagnosis of clinically significant macular edema
- Confirmed diagnosis of active tuberculosis (TB)
- Subjects who have a cardiovascular treatment-related symptomatic event (eg, chest pain, dizziness, palpitations, lightheadedness, shortness of breath, or syncope) associated with reduction of the heart rate or associated with clinically relevant ECG changes at any time during the 4-hour monitoring period on the first or second day after re-initiation of treatment after a dose interruption of ≥ 7 days (Section 9.4.1)
- Subjects who have not met the discharge criteria on the first day of re-initiation of treatment after ≥ 4 hours of extended monitoring, or on the second day of re-initiation by 4 hours postdose.
- Pregnancy (Section 9.8.9)
- Suspected drug-induced liver injury as defined by the 2009 FDA Guidance for Industry (FDA 2009):
 - Alanine aminotransferase (ALT) or aspartate aminotransferase (AST) > 8 × upper limit of normal (ULN)
 - ALT or AST $> 5 \times ULN$ for > 2 weeks

- ALT or AST $> 3 \times$ ULN and (total bilirubin $> 2 \times$ ULN or international normalized ratio > 1.5)
- ALT or AST $> 3 \times$ ULN with the appearance of fatigue, nausea, vomiting, right upper quadrant pain or tenderness, fever, rash, and/or eosinophilia (> 5%)

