5.2. Discontinuation from the Study

Subjects may be discontinued from the study at any time for any of the following reasons:

- Withdrawal by subject or parent/guardian
- Deviation/noncompliance with the study protocol that in the judgement of the Investigator and/or Medical Monitor the subject should not continue study treatment
- Study termination by Sponsor
- Lost to follow-up
- Death
- Other

A subject may withdraw from the study at any time for any reason without prejudice to their future medical care by the physician or at the institution. If a subject withdraws consent, no further evaluation should be performed, and no additional data should be collected. The Sponsor may retain and continue to use any data collected before such withdrawal of consent. The Investigator should make a reasonable attempt to document the specific reason why consent was withdrawn.

In the event that a subject fails to attend any follow-up visits, all reasonable efforts will be made to contact the subject to ensure that he/she is in satisfactory health. All contacts and contact attempts must be documented in the subject's file.

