10.4. Missing Data

Subjects with worsening of disease, as defined in Section 5.1.1, will be considered as having a treatment nonresponse outcome in the analysis of all endpoints, including the primary endpoint.

In addition, subjects who initiate an agent not allowed in combination with the study treatment that can affect the efficacy of the study treatment, such as an immunosuppressant or corticosteroid, or who have an increase in dose over baseline levels for treatment of worsening disease symptoms will be considered non-responders thereafter or be handled by per protocol analysis.

Subjects discussed above will be considered as having a known outcome at the analysis timepoint (ie, a treatment failure outcome) and not as having missing data. Subjects who discontinue the double-blind study for reasons other than worsening disease or adverse event related to UC will be considered as having missing data and will be handled in the primary and sensitivity analyses as follows.

A full description of the handling of missing data will be provided in the SAP.

Primary Method of Handling Missing Data

In the primary analysis of the primary endpoint and main analyses of all binary responder-type endpoints, all subjects with missing data, regardless of reason for missingness, will be considered as non-responders.

In the main analysis of continuous or score endpoints, such as changes from baseline in MMS subscores, biomarker measures, urgency NRS, abdominal pain NRS, and health-related quality of life measures, subjects with missing data will be handled using last observation carry forward, or a mixed-effect model with repeated measures. Detailed methods will be provided in the SAP.

Sensitivity Analyses for Missing Data

Sensitivity analyses may be performed under several alternative assumptions regarding missing data, ie, data missing intermittently, after discontinuation from the double-blind study for reasons other than worsening diseases, or after initiation of excluded medications.

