16.1.4. Supplementary Analysis of Primary Efficacy Variables

The primary analysis as described in Section 16.1.3 will be repeated using the mFAS (with data as observed) as supplementary analyses.

Key Secondary Efficacy

Key secondary efficacy endpoints are defined in Section 16.2. In general, all the primary and supplementary analyses planned for the primary endpoints in Section 16.1.3 and Section 16.1.4 will be repeated for each key secondary efficacy endpoint (Table 3). No Multiplicity adjustments will be conducted as discussed in Section 8.4.

Table 3 Planned Analyses by Endpoint

Endpoint	Primary Analysis in FAS	Supplementary Analyses in mFAS
Primary endpoint: Clinical remission at Week 52	X	X
Key secondary endpoints:		
Endoscopic improvement at Week 52	X	X
Symptomatic remission at Week 52	X	X
Corticosteroid-free clinical remission at Week 52	X	X
Mucosal healing at Week 52	X	X
Sustained clinical remission at Week 12 and at Week 52	X	X

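### The SAP omits, without declaring it, the protocol's rule that disease worsening is a known nonresponse, so exits recorded only as worsening can leave the as-observed mFAS denominator at Week 52

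*SAP*

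**What the plan says.** Protocol 10.4 sets the rule: "Subjects with worsening of disease, as defined in Section 5.1.1, will be considered as having a treatment nonresponse outcome". It covers all endpoints, and the section adds that these subjects have a known outcome rather than missing data. The complement is also spelled out. Only those who "discontinue the double-blind study for reasons other than worsening disease or adverse event related to UC will be considered as having missing data".

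SAP 16.1.2 replaces this with four triggers for known nonresponse. The first is for subjects who "discontinue the study for lack of efficacy, or adverse event related to UC". The next two are to "initiate a rescue medication for UC, 3) have an increase in dose over Baseline levels in their existing UC medication", and the fourth is a rescue medical procedure. Worsening as defined in Protocol 5.1.1 is not among them.

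SAP Table 1 omits it too. Its intercurrent-event column puts discontinuation for lack of efficacy or a UC-related adverse event under missing data, and its footnote lists only rescue medication, dose increase, and colectomy or ileostomy. SAP 3.3, which lists changes from the protocol, reports the UC-PRO/SS and CMH changes only.

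In Protocol 5.1, worsening has its own entry among the reasons for stopping treatment: "Worsening of disease (Note: If a subject discontinues double-blind treatment at any time". Lack of efficacy is a separate entry in the same list.

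The FAS analysis imputes missing outcomes as nonresponse (SAP 8.3 and 16.1.2). SAP 16.1.4 then says that the primary analysis "will be repeated using the mFAS (with data as observed) as supplementary analyses". SAP 5.4 drops Per Protocol efficacy analyses, so Table 3 is left with the mFAS alone.

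**The concern.** Leaving for the open-label study because of worsening is a foreseen route out of this trial, and it is a treatment failure by the protocol's own definition. An as-observed analysis is acceptable only if known failures stay in it as failures. If some are handled as absent data, each arm's remission rate is computed on a denominator from which failures have been removed. The removal depends on outcome and may differ by arm. In a trial of about 35 subjects a few such exits can change the supplementary result noticeably. That result is the only check on the primary analysis that the SAP retains. Because SAP 3.3 is silent, a reader of the study report would also not know that the protocol's rule had been dropped.

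**Working it through.** The documents give no figure on this point, so there is none to reproduce. The check has two parts: following one subject through the rules, and an illustration on assumed counts.

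**Following one subject.** Take a subject who stops before Day 337, enters the open-label study, and has worsening of disease as the only recorded reason.

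1. Protocol 10.4: known nonresponse at Week 52.
2. SAP 16.1.2, trigger 1: not met on its wording, unless the reason is coded or reviewed as lack of efficacy or a UC-related adverse event. Triggers 2 to 4: not met.
3. SAP 6.4, Table 2: endpoints built on any Mayo component use Day 337 to 393 for Week 52 (to Day 421 if affected by COVID-19). An earlier exit assessment does not map to Week 52.
4. FAS: Week 52 is missing and is imputed as nonresponse. The result is the same as under the protocol.
5. mFAS as observed: nothing is imputed, and SAP 6.6 divides by the number of subjects at the visit. The subject is not in the denominator.

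The two documents therefore agree for this subject in the FAS and part company in the mFAS.

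**Illustration.** From the documents: about 35 subjects (Protocol 10.2) and 2:1 allocation (Protocol 6.1), so 35 × 2/3 = 23.3 and 35 × 1/3 = 11.7, taken as 23 and 12. Assumed: 8 remitters on etrasimod and 2 on placebo; worsening-only exits wE and wP, all non-remitters before Day 337; everyone else observed at Week 52.

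- Exits counted as failures: 8/23 − 2/12 = 34.8% − 16.7% = 18.1 points.
- Exits dropped: 8/(23 − wE) − 2/(12 − wP).

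| Exits (etrasimod, placebo) | Etrasimod | Placebo | Difference |
|---|---|---|---|
| 4, 7 | 8/19 = 42.1% | 2/5 = 40.0% | 2.1 |
| 5, 6 | 8/18 = 44.4% | 2/6 = 33.3% | 11.1 |
| 3, 4 | 8/20 = 40.0% | 2/8 = 25.0% | 15.0 |
| 5, 3 | 8/18 = 44.4% | 2/9 = 22.2% | 22.2 |

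Dropping exits raises both rates, and the difference moves according to which arm rises more. With 5 and 6 exits, etrasimod rises by 9.7 points and placebo by 16.7, so the difference falls by 7.0. With 5 and 3, the rises are 9.7 and 5.6, so it grows by 4.1. In that last row exits are still more frequent on placebo (3/12 = 25.0% against 5/23 = 21.7%), so more exits on placebo does not settle the direction.

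A different assumption, 9 and 2 remitters, gives an FAS difference of 9/23 − 2/12 = 22.5 points. As observed, it is 9/21 − 2/4 = −7.1 with 2 and 8 exits, and 9/17 − 2/9 = 30.7 with 6 and 3.

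**The case against.** The strongest reply is that the SAP's term may cover the same people. Protocol 5.1.1 applies to subjects who have failed to improve as well as to those who have worsened, and failure to improve is lack of efficacy. Worsening of a pre-existing condition can be an adverse event (Protocol 9.8.8.1.1), and a UC-related adverse event is in trigger 1. Rescue, dose increase and procedures catch others. An exit assessed inside the Week 52 window is observed, not missing. All of this stands, and it limits the problem to exits recorded solely as worsening. It does not remove the problem: Protocol 5.1 keeps the two reasons apart, and nothing in either document maps one to the other.

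Four stronger readings are tempting and not supported:

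- *Trigger 1 catches almost nobody, because Protocol 5.2 lists neither lack of efficacy nor adverse events as reasons for leaving the study.* Protocol 10.4 itself treats worsening and UC-related adverse events as reasons for leaving the double-blind study, 5.2 has an open category for other reasons, and Table 1 is not worded as study discontinuation. The treatment/study distinction is used loosely in both documents.
- *The primary result is compromised.* Nonresponder imputation covers exits without Week 52 data. A late exit with a centrally read ES ≤ 1 in the window could count as endoscopic improvement, or as mucosal healing if histology agrees. However, entry to the open-label study for worsening requires an ES that contradicts such a reading, so this exception is remote and concerns the endoscopic endpoints.
- *The supplementary analysis is biased against the drug.* The last row of the table shows movement the other way.
- *Subjects who met the worsening criteria, stayed in and remitted are misclassified in the FAS.* Protocol 10.4 does not mention exit, but Protocol 5.1.1, which it cites, is headed and written as a rule on discontinuation. The point does not rest on this reading.

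**Conclusion.** The omission is real and undeclared. Its effect is confined, in practice, to the as-observed mFAS analyses at Week 52 and to subjects whose exit is recorded only as worsening, with no other trigger and no assessment in the window. How many there will be cannot be told from the documents, because the eCRF reason categories and the blinded-review mapping are not shown. On the assumed 23:12 split with 8 and 2 remitters, the mFAS difference ran from 2.1 to 22.2 points against 18.1 in the FAS. The counts are illustrative; only the planned total and the allocation ratio come from the documents, and the ratio is not controlled within Japan. The study has no formal sample size and reports only nominal p-values, so no formal test decision turns on this. The change is still worth making, because it restores the protocol's own rule in the only supplementary analysis that remains.

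**What to change.** - In SAP 16.1.2 item 1 and in Table 1, add discontinuation of double-blind treatment or of the study for worsening of disease (Protocol 5.1.1), alongside lack of efficacy and UC-related adverse event. State that it is a known nonresponse at all subsequent timepoints in both the FAS and the mFAS.
- Derive it from the end-of-treatment or end-of-study reason and the disease-worsening CRF. SAP 5.5 shows that this form exists. It bars the form's manually entered Mayo scores from the mFAS derivation, but a worsening flag does not need those scores.
- Align Table 1, which groups these discontinuations with missing data, with 16.1.2, which calls them non-missing.
- If the departure from Protocol 10.4 is intended, declare and justify it in SAP 3.3 instead.

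The cost is one SAP sentence, the matching Table 1 entry and one programming flag. No new data are needed.

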16.1.3. Primary Analysis of Primary Efficacy Variable

The primary efficacy analysis will be performed for the FAS. Results will be expressed as the number and percentage of subjects in remission, difference in remission percentages and 95% CI and nominal p-value from Fisher's Exact test, odds ratio and 95% CI.

16.1.4. Supplementary Analysis of Primary Efficacy Variables

The primary analysis as described in Section 16.1.3 will be repeated using the mFAS (with data as observed) as supplementary analyses.

Key Secondary Efficacy

Key secondary efficacy endpoints are defined in Section 16.2. In general, all the primary and supplementary analyses planned for the primary endpoints in Section 16.1.3 and Section 16.1.4 will be repeated for each key secondary efficacy endpoint (Table 3). No Multiplicity adjustments will be conducted as discussed in Section 8.4.

Table 3 Planned Analyses by Endpoint

Endpoint	Primary Analysis in FAS	Supplementary Analyses in mFAS
Primary endpoint: Clinical remission at Week 52	X	X
Key secondary endpoints:		
Endoscopic improvement at Week 52	X	X
Symptomatic remission at Week 52	X	X
Corticosteroid-free clinical remission at Week 52	X	X
Mucosal healing at Week 52	X	X
Sustained clinical remission at Week 12 and at Week 52	X	X

16.1.5. Key Secondary Efficacy Variables and Derivations

- Endoscopic Improvement at Week 52.
- Symptomatic Remission at Week 52.

- Corticosteroid-Free Clinical Remission at Week 52.
- Mucosal Healing at Week 52.
- Sustained Clinical Remission (*i.e.*, at both Week 12 in APD334-302 and Week 52 in APD334-308).

There is no multiplicity adjustment in examining any of the key secondary efficacy variables and derivations stated above.

16.1.6. Missing Data Methods for Key Secondary Efficacy Variables

In general, the same missing data methods used for the primary endpoints in Section 16.1.2 will be used for the key secondary endpoints.

16.1.7. Primary Analysis of Key Secondary Efficacy Variables

The primary analysis of these key secondary efficacy endpoints will be performed for the FAS. For all key secondary endpoints, the model described in Section 16.1.3 will be used.

16.1.8. Supplementary Analysis of Key Secondary Efficacy Variables

For all key secondary endpoints, the primary model as described in Section 16.1.3 Section will be repeated using the mFAS (with data as observed) as supplementary analyses.

16.2. Other Secondary Efficacy Variables and Derivations

Other secondary efficacy endpoints are defined in Section 16.

- The proportion of subjects achieving clinical response at Week 52
- The proportion of subjects achieving endoscopic normalization at Week 52
- The proportion of subjects achieving symptomatic remission at Weeks 16, 20, 24, 32, 40, 48 and 52
- The proportion of subjects achieving complete symptomatic remission at each study visit (Weeks 16, 20, 24, 32, 40, 48, and 52)
- The proportion of subjects achieving noninvasive clinical response at each study visit (Weeks 16, 20, 24, 32, 40, 48, and 52)
- The proportion of subjects achieving symptomatic response at each study visit (Weeks 16, 20, 24, 32, 40, 48, and 52)

[figure not shown]
16.2.1. Missing Data Methods for Other Secondary Efficacy Variables

All subjects with missing data, regardless of reason for missingness, will be considered as nonresponders. The intercurrent events that are considered in the primary efficacy analysis will be handled similarly for the other secondary efficacy endpoints, as specified in Section 16.1.2.

16.2.2. Analysis of Other Secondary Efficacy Variables

The analysis of other secondary efficacy endpoints will be performed for the FAS. The primary analysis method planned for the primary endpoints in Section 16.1.3 will be repeated for each other secondary efficacy endpoint.

CCI

CCI

17. HEALTH-RELATED QUALITY OF LIFE AND HEALTHCARE RESOURCE UTILIZATION ANALYSIS

Subject reported HRQoL instruments will be electronically captured and used in support of the efficacy outcomes. All HRQoL are administered at Week 52/Early Termination Visit. The HRQoL analyses will be performed using the mFAS data as observed.

All HRQoL endpoints will be analyzed using descriptive statistics (n, mean, SD, median, minimum, and maximum)

Healthcare resource utilization endpoints, ie, the proportion of concomitant UC-related hospitalizations and the proportion of concomitant UC-related surgeries, including colectomy, will be analyzed using the analysis method described in Section 16.1.3.

17.1. VARIABLES & DERIVATIONS

17.1.1. INFLAMMATORY BOWEL DISEASE QUESTIONNAIRE [IBDQ]

The IBDQ is a 32-item self-administered questionnaire which has 4 dimensions: bowel symptoms (10 items), systemic symptoms (5 items), emotional health (12 items), and social function (5 items). Responses are graded on a 7-point Likert scale where 7 denotes “not a problem at all” and 1 denotes “a very severe problem”. Scores range from 32 to 224, a higher score indicates better quality of life.

The IBDQ total score and 4 domain subscores will be derived on the eCRF directly. Details about scoring rules can be found in APPENDIX 3.

17.1.2. 36-ITEM SHORT FORM HEALTH SURVEY, VERSION 2

The 36-Item Short Form Health Survey (SF-36) is a 36 item, subject-reported survey of subject health. The SF-36 consists of 36 questions measuring 8 health domains: Physical functioning, bodily pain, role limitations due to physical problems, role limitations due to emotional problems, general health perceptions, mental health, social function, and vitality. The subject’s responses are solicited using Likert scales that vary in length, with 3 to 6 response options per item. The SF-36 will also be scored using 2 overall summary scores: Physical component summary (PCS) and mental component summary (MCS) scores. A higher score indicates better health status.

The Physical Component Summary Score (norm based), the Mental Component Summary Score (norm based), 8 domain subscores (0 to 100 based), and the SF-6D health utility index score are derived by Optum and integrated into the SF-36 eCRF. Details about domain scores can be found in APPENDIX 4.

